1 FLOW CHARTS

1.1 STUDY FLOW CHART

Table 1 - Schedule of assessments: screening to Day 63 (Times are post-dose)

Evaluation	Screen/ Predose	Treatment Period and post-treatment surveillance														Follow-Up (FU)													
		V2										V3		V4	V5	V6	V7	V8	V9	V10	V11	V12	V13	V14	V15 (EOS)				
Visits (V)	V1											1		2	3	5	7	10	14	15- 18 ^g	21 +/- 2	24- 25 ^g	28 +/- 2	42 +/- 3	63 +/- 3				
Day ^a	-1	0										1		2	3	5	7	10	14	15- 18 ^g	21 +/- 2	24- 25 ^g	28 +/- 2	42 +/- 3	63 +/- 3				
Hours		0	0.5	1	2	4	6	8	12	18	24	30	36	48	72														
Informed consent	X																												
Demography, medical history	X																												
Inclusion/exclusion criteria	X																												
IVRS/IWRS call	X	X																								X			
Randomization		X																											
Hospitalization ^b		→																											
Visit at clinical site																X	X	X	X	X	(X)	X	(X)	X	X	X			
Treatment																													
OZ439 ^c		X																											
FQ ^c		X																											
Prior and concomitant medication	X	X								X				X	X	X	X	X	X	X	X	X	X	X	X	X			

Evaluation	Screen/ Predose	Treatment Period and post-treatment surveillance														Follow-Up (FU)											
		V2										V3				V4	V5	V6	V7	V8	V9	V10	V11	V12	V13	V14	V15 (EOS)
Visits (V)	V1	0										1				2	3	5	7	10	14	15- 18 ^g	21 +/- 2	24- 25 ^g	28 +/- 2	42 +/- 3	63 +/- 3
Day ^a	-1	0										1				2	3	5	7	10	14	15- 18 ^g	21 +/- 2	24- 25 ^g	28 +/- 2	42 +/- 3	63 +/- 3
Hours		0	0.5	1	2	4	6	8	12	18	24	30	36	48	72												
Efficacy																											
Physical exam & malaria signs & symptoms	X								X		X		X	X	X		X								X	X	X
Weight ⁱ	X													(X)	(X)												X
Temperature (single) ^d	X			X	X		X		X	X	X	X	X	X	X	X	X	X	X	X	X	X	X	X	X	X	X
Asexual & sexual count (thick & thin blood films) >14 y and ≥35 kg (Cohort 1) ^d	X ^e					X		X	X	X	X	X	X	X	X	X	X	X	(X)	X	(X)	X	X	X	X	X	
Asexual & sexual count (thick & thin blood films) ≤14 years (Cohorts 2 to 4) ^d	X ^e					X		X	X		X	X	X	X	X	X	X	X	(X)	X	(X)	X	X	X	X	X	
qPCR, parasite genotyping & RT-PCR gametocyte detection sampling >14 y and ≥35 kg (Cohort 1) ^f	X ^e					X		X	X	X	X	X	X	X	X	X	X	X	(X)	X	(X)	X	X	X	X	X	

Evaluation	Screen/ Predose	Treatment Period and post-treatment surveillance														Follow-Up (FU)										
		V2									V3			V4	V5	V6	V7	V8	V9	V10	V11	V12	V13	V14	V15 (EOS)	
Visits (V)	V1	0									1			2	3	5	7	10	14	15- 18 ^g	21 +/- 2	24- 25 ^g	28 +/- 2	42 +/- 3	63 +/- 3	

- a* At each patient visit/contact post dose, antimalarial rescue therapy conditions will be assessed and rescue therapy may be given accordingly.
- b* Discharge at 48 hours (African patients > 5 years) or 72 hours (all other patients) (or up to Day 7) depending on age, parasite and fever clearance, clinical judgment and patient convenience. If discharged prior to Day 7, will return to Investigational site for further assessment on all scheduled times up to Day 7.
- c* Patients should have fasted from food and milk for 3 hours before administration. Neither food nor milk should be taken within 2 hour after the end of IMP dosing.
- d* Blood films (thick and thin, performed locally) and temperature measurements need to be confirmed as follows: when 1st parasite clearance or 1st temperature <37.5 °C, measurements need to be confirmed with second reading 6 to 12 hours after the 1st measurement (ie, to determine Parasite Clearance or Fever Clearance). The first measurement (if confirmed) will be considered the 'Clearance Time'. Only asexual count will be used as parasitemia for evaluation of study endpoints. If parasites have not cleared by 72 hours after IMP administration and criteria for rescue medication are not met at 72 h, blood films should continue to be taken according to site standard practice (or at minimum every 8 hours) until parasite clearance is shown or until criteria for rescue medication are met (see [Section 8.9](#)). If these additional blood smears are taken they should be recorded as unscheduled visits in the CRF.
- Note: Axillary temperature should be recorded. If the axillary method is not possible, an alternative route (tympenic, oral, rectal) may be used. Within an individual patient the same method of temperature measure should be used throughout the study.
- e* Measurement required within 4 hours prior to dosing. Local thick and thin blood films performed at the site, before Informed Consent signature, according to local standard procedures, can be used as screening / Pre-dose parasitaemia assessments ([Section 9.3.1.1](#)) provided that a standard procedure is in place at site and blood films stainings are performed according to Study Parasitology Procedures Manual.
- f* Blood spots or blood sample for qPCR (patients >5 y only), blood spot for parasite genotyping and Kelch-13 analysis; blood sample for RT-PCR gametocyte detection (patients >5 y only). To be collected, according to the schedule and the instructions reported in the Study Laboratory Procedures Manual. Parasite genotyping analysis will be performed on previously collected blood spot sample only in case of a positive blood film after initial parasite clearance: one pre-dose sample and one sample at 18 or 24 hours post dosing. A further sample will be analyzed at the time point at which recrudescence/re-infection occurs (if applicable). Sample for Kelch-13 analysis at baseline only. All of these tests will be performed in central lab. During the intervening periods between V10 and V12, blood for RT-PCR gametocyte detection and qPCR (patients >14 years and ≥35kg only) will only be taken if the patient returns to the site for assessment. (see [9](#)). An additional blood sample (susceptibility testing) will be taken in patients >14 years old in Vietnamese sites at screening (6 mL) and when criteria for rescue treatment for malaria is met (6 mL). These samples will be used for in vitro research of drug resistance (see [Section 9.4.2](#)).
- g* Patients will have one additional safety check at V10 and V12. Patients may either return to the Investigational site or tests can be performed in the field by trained persons. If returning to the Investigational site, a blood film (thick and thin), a genotyping sample and temperature should be taken. Sample for qPCR and, RT-PCR should be taken for patients >14 years and ≥35 kg only. For patients remaining in the field, a malaria RDT and temperature should be taken. Patients feeling unwell, with increased temperature (axillary temperature ≥37.5 °C) and/or a positive RDT should return to the Investigational site for assessment including blood films, parasite genotyping.
- h* Deleted.
- i* Patients should rest supine prior to measurement for a minimum of 10 minutes (or at least 5 minutes for blood pressure measurement).
Single ECG will be taken at screening. Triplicate ECGs will be taken at T0 (before IMP administration) and at all time-points thereafter. Depending on discharge date, triplicate ECG to be performed at D2 or D3. For all African patients of Cohort 1, triplicate ECG to be performed at D2 (PK/QTc purpose). For all patients discharged after D3, triplicate ECG should be performed at D3.
Body weight at screening, discharge (D2 or D3) and EOS. For all patients discharged after D3, body weight and vital signs should be performed at D3. Height at screening for BMI calculation.
- j* Laboratory safety: hematology (local), clinical chemistry (screening: one local lab sample for inclusion criteria and one central lab sample for baseline values; central lab samples at all time-points thereafter), and urinary dipstick (performed locally; if any parameter on the dipstick is abnormal, a urine sample should be sent to the central lab for microscopic analysis) (See [Table 4](#) for details). Depending on discharge date, laboratory safety at D2 or D3. For all patients discharged after D3, sample should be taken at D3. No sample will be taken at V11 (D21+/-2) for children ≤ 5 years.
- k* Serology: Test for hepatitis by rapid spot test: HAV IgM, HBs Ag and HCV Ab.
- l* Urine HCG is the minimum acceptable test. It will be performed locally. Result must be confirmed negative prior to dosing and must be consistent with menstrual history.
- m* Where time points coincide, PK sampling should be performed after vital signs, temperature and ECG measurement. Blood samples will be collected within ± 15 minutes of nominal time until 48 h after administration. The exact date and time should be recorded at all PK sampling time points.
For FQ PK samplings, blood will be collected by venipuncture for Dried Blood Spot (DBS) assay (all sites). In selected sites, plasma (Dried Plasma Spot, DPS) assay will also be performed in a sub-set of patients.

[figure not shown]
Note: For FQ PK samplings, "BPXX" indicate DBS sample, "PPXX" indicate DPS sample. For OZ PK samplings, "PYY" indicates a plasma OZ PK sample.

For patients > 6 months and ≤5 years, FQ PK sampling will consist of 3 different sampling schedules (Group 1, Group 2, Group 3) attributed at random by the IVRS/IWRS. PP00, PP01 and PP02 only for children >2 years. In addition, for all patients where possible, a PK (OZ and FQ) sample should be obtained when a rescue treatment for malaria is given or when QTcF>500 ms or QTcF prolongation >60 ms from baseline or when ALT increase (see [Section 10.4.1.4](#)). Those additional samples will be identified as "BPA01" for DBS of FQ and as "PA01" for plasma sample of OZ.

Note: Visit 1 & Visit 2 can occur on the same day, provided that all baseline assessments and biology (including parasitemia and laboratory safety) results are obtained, before patient randomization. Visits or examinations presented in brackets have to be performed when applicable.

1.2 STEP-DOWN AND STEP-UP PROCEDURES

Figure 1 - DMC safety review for age step-down & FQ dose step-up procedures

Scenario A: design with 3 treatment arms (OZ439/FQ 800/400 mg, 800/600 mg and 800/900 mg) if 4th treatment arm (OZ439/FQ 800/1200 mg) not started after DMC review at the end of Cohort 1a or stopped after DMC review at the end of Cohort 1b.

Scenario B: design with 4 treatment arms (OZ439/FQ 800/400 mg, 800/600 mg, 800/900 mg and 800/1200 mg) if 4th treatment arm (OZ439/FQ 800/1200 mg) started and continued after DMC reviews at the end of Cohorts 1a & 1b respectively.

- Patients ≥ 35 kg:
 - Treatment arm 1 = OZ439 800 mg - FQ 400 mg,
 - Treatment arm 2 = OZ439 800 mg - FQ 600 mg,
 - Treatment arm 3 = OZ439 800 mg - FQ 900 mg,
 - Treatment arm 4 = OZ439 800 mg - FQ 1200 mg

- Patients <35 kg will receive
 - Weight-adjusted doses for OZ439 predicted to achieve exposure (based on AUC) not exceeding 1.5-fold that of a 60 kg adult and not exceeding that of the lightest adult (35 kg) for the lightest patient in each weight band.
 - Weight adjusted doses for FQ predicted to achieve FQ and SSR97213 exposure (based on mean C_{max} and AUC) not exceeding 1.3-fold that of a lightest adult (35 kg) for the lightest patient in each weight band.

*: A minimum number of 10 patients (Cohort 1) per treatment arm for DMC safety & PK/QTc evaluation

**.: A minimum number of 5 patients (Cohort 2) per treatment arm for DMC review

***.: A minimum number of 8 patients (Cohorts 3 & 4) per treatment arm for DMC review

After all these age step-down stages, the recruitment will be fully open. Approximately 62 patients will be recruited in Cohorts 1 and 2 for Scenario B. The remaining patients will comprise Cohorts 3 and 4. At least 10% of the lower NAI population will come from African patients of Cohort 4.

[figure not shown]
****.: DMC review before starting Cohort 2 recruitment will be made on pooled data (Cohorts 1a & 1b) with a total number of patients $N \geq 42$.

Notes:

- **Patients likely to have higher NAI (African patients >5 years old to <70 years old) and Asian patients will only be considered for safety review.**
- **African patients likely to have lower NAI (children ≤ 5 years) will be considered for safety review, and also fertility and efficacy analyses.**

For DMC safety review, no predefined ratio between African and Asian patients is requested to move forward from one group of age to the next one. Patients will be included following a “competitive recruitment” process.

Figure 2 - Futility interim analysis

* Futility analysis will be conducted by the DMC statistician

3 LIST OF ABBREVIATIONS

° C:	degrees Celsius
ACPR:	adequate clinical and parasitological response
ACT:	artemisinin-based combined therapy
AESI:	adverse event of special interest
AS:	artesunate
BP:	blood pressure
CRF:	case report form
DBS:	dry blood sample
DMC:	data monitoring committee
DPS:	dry plasma sample
DRF:	discrepancies resolution form
e-CRF:	electronic case report form
ETF:	early treatment failure
FCT:	fever clearance time
FQ:	ferroquine
GCP:	good clinical practices
HR:	heart rate
IA:	interim analysis
ICH:	International Conference of Harmonization
IMP:	investigational medicinal product
IRB/IEC:	institutional review board/independent ethics committee
LCF:	late clinical failure
LFT:	liver function test
LOQ:	limit of quantification
LPF:	late parasitological failure
MMV:	Medicines for Malaria Venture
MPC:	minimum parasitocidal concentration
ms:	millisecond
NAI:	naturally acquired immunity
OZ439:	artefenomel
P. falciparum :	Plasmodium falciparum
PCR:	polymerase chain reaction
PCT:	parasite clearance time
PK:	pharmacokinetic
PRR:	parasite reduction rate
RDT:	rapid diagnostic test
SAE:	serious adverse event
SUSAR:	suspected unexpected serious adverse reaction
TEAE:	treatment emergent adverse event
TPGS:	alpha tocopherol polyethylene glycol 1000 succinate
WHO:	World Health Organization

GLOSSARY OF TERMS

qPCR (quantitative polymerase chain reaction)

A polymerase chain reaction procedure is used to quantify the amount of *Plasmodium falciparum* (*P. falciparum*)-specific DNA present and is transformed into number of parasites/ μ L.

RT-PCR (reverse transcriptase polymerase chain reaction)

Gametocytes are differentiated from asexual forms by targeting RNA transcripts of gametocyte-specifically expressed genes (Pfs25).

Recrudescence

Recrudescence is defined as the appearance of asexual parasites after clearance of initial infection with a genotype identical to that of parasites present at baseline. Recrudescence must be confirmed by microscopy (positive blood smear) and polymerase chain reaction (PCR) analysis.

Re-infection

Re-infection is defined as the appearance of asexual parasites after clearance of initial infection with a genotype that differs from that of parasites present at baseline. Re-infection must be confirmed by microscopy (positive blood smear) and PCR analysis. Confirmed new infection will not be regarded as treatment failure or recrudescence.

Re-emergence/Recurrence

Re-emergence (recrudescence and re-infection) is defined as the appearance of asexual parasites after clearance of initial infection irrespective of genotype.

PCR crude

PCR-crude adequate clinical and parasitological response (ACPR) does not distinguish between re-infection (by a new clone of parasite) and recrudescence (re-emergence of the original clone of parasite that is present at baseline).

PCR-adjusted

PCR-adjusted ACPR applies only to recrudescence (re-emergence of the original clone of parasite that is present at baseline). Recrudescence is distinguished from re-infection by genotyping the parasite clone.

SSR97213

N-demethyl derivative, active metabolite of ferroquine (FQ)

CLASSIFICATION OF TREATMENT OUTCOMES (ADAPTED FROM WHO, 2009) (1)

Parasitemia will be evaluated locally with blood smear.

Early treatment failure (one the following)

- Danger signs or severe malaria on Day 1, 2 or 3 in the presence of parasitemia;
- Parasite count on Day 2 higher than on Day 0, irrespective of axillary temperature;
- Parasitemia on Day 3 with axillary temperature $\geq 37.5^{\circ}\text{C}$;
- Parasite count on Day 3 $\geq 25\%$ on Day 0.

Late clinical failure

- Danger signs or severe malaria on any day between Day 4 and Day 63 in the presence of parasitemia, without previously meeting any of the criteria of early treatment failure;
- Presence of parasitemia and axillary temperature ≥ 37.5 degrees Celsius ($^{\circ}\text{C}$) (or history of fever) on any day between Day 4 and Day 63, without previously meeting any of the criteria of early treatment failure.

Late parasitological failure

- Presence of parasitemia on any day between Day 7 and Day 63 and axillary temperature $< 37.5^{\circ}\text{C}$, without previously meeting any of the criteria of early treatment failure or late clinical failure.

Adequate clinical and parasitological response (ACPR)

- Absence of parasitemia on Day 28 (or Day 42 or Day 63), irrespective of axillary temperature, without previously meeting any of the criteria of early treatment failure or late clinical failure or late parasitological failure.

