9.3.1.2 Post-dose blood films

Three slides (two thick films and one thin film) should be prepared at each planned time point (see Study Flow-Chart in [Section 1.1](#) for detailed time schedule). The first thick film slide should be stained with 2.5 to 3% Giemsa stain for a period of 45 to 60 minutes and used to determine parasite counts. The second thick film slide should be kept as contingency and be stained only if the first thick film slide become damaged prior to reading it. The thin film slide is used specifically for parasite speciation which should be recorded at each time point.

Additional unscheduled films may be prepared to confirm Parasite clearance as described below.

Details of slide preparation, staining, examination, calculation methods and quality control are given in the Study Laboratory Procedures Manual. No deviation from the Sponsor guidelines will be accepted.

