9.3.1.3 Definition of parasite clearance (by microscopy)

A blood film will be considered 'negative' when the examination of 1000 white blood cells reveals no asexual parasites (see Study Laboratory Procedures Manual for more detail). Parasite clearance time is defined as the time of the first negative film. This negative film must be confirmed by a second negative film, prepared within 6 to 12 hours of the first. Parasite clearance will be concluded following confirmation of the second negative film. Parasite density, expressed as the number of parasites per microliter of blood, for asexual parasite and for gametocyte counts will be recorded separately throughout the study.

If parasites have not cleared by 72 hours after IMP administration and criteria for rescue medication are not met at 72 h, blood films should continue to be taken according to site standard practice (or at minimum every 8 hours) until parasite clearance is shown or until criteria for rescue medication are met (see [Section 8.9](#)).

Two qualified microscopists should independently read the stained thick and thin films. Parasite densities will be calculated by averaging the two counts. Blood smears with non-concordant results (differences between the two microscopists in species diagnosis, or differences in parasite density of >50%) will be re-examined by a third, independent microscopist: if discordance relates to parasite density, it will be calculated by averaging the two most concordant counts; if discordance relates to species diagnosis, it will be determined by the third microscopist.

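### The failure, negative-film and re-emergence definitions name no Plasmodium species, so a new non-falciparum infection counts against PCR-crude ACPR and time to re-emergence, and its place in the primary endpoint is not settled

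*Protocol*

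**What the plan says.** **Target.** The primary objective (Section 5.1) is treatment of uncomplicated P. falciparum malaria. Inclusion criterion I 03 requires falciparum mono-infection, and E 05 excludes mixed infection at entry.

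**Outcome rules.** The classification of treatment outcomes (end of Section 3) defines:
- late parasitological failure by "Presence of parasitemia on any day between Day 7 and Day 63" in an afebrile patient;
- late clinical failure by "Presence of parasitemia and axillary temperature" at or above the fever limit, or a history of fever, from Day 4;
- ACPR by "Absence of parasitemia on Day 28 (or Day 42 or Day 63), irrespective of axillary temperature", with no earlier failure.

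Re-emergence in the glossary is "the appearance of asexual parasites after clearance of initial infection irrespective of genotype". A film is negative under Section 9.3.1.3 when "the examination of 1000 white blood cells reveals no asexual parasites". Flow-chart footnote d adds: "Only asexual count will be used as parasitemia for evaluation of study endpoints". That restricts by parasite stage, not by species.

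**Species data.** Section 9.3.1.2 says: "The thin film slide is used specifically for parasite speciation which should be recorded at each time point". Section 9.3.1.3 sends disagreement on species to a third microscopist. No outcome definition uses the result.

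**Clauses that limit the problem.** The glossary defines re-infection by a genotype different from baseline, requires confirmation by smear and PCR, and says that a confirmed new infection is neither a failure nor a recrudescence. Section 9.1.1 confines PCR-adjusted ACPR to recrudescence of the baseline clone. The same section also withholds ACPR from a patient given rescue treatment under Section 8.9, which recommends rescue for any failure in the classification above.

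**The concern.** An infection with another species acquired during follow-up says nothing about whether the falciparum infection was cured. Yet a film showing asexual parasites of any species satisfies the failure wording, cannot be a negative film, and is a re-emergence.

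Two things are at stake:
- **Secondary endpoints.** PCR-crude ACPR and time to re-emergence would mix falciparum recurrence with unrelated infections. Section 11.4.3.2 plans a dose-response evaluation on crude ACPR, and Section 4.2.2 used uncorrected cure rates from an earlier study to justify testing doses above 600 mg.
- **Primary endpoint.** The protocol does not say how such a child is classified, so two analysts could differ. With few failures allowed per arm, that choice should not be left open.

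**Working it through.** **1. One child traced through the rules.** Take a child aged 5 years or less, cleared of falciparum, afebrile, whose Day 21 film shows asexual parasites of another Plasmodium species.

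| Rule | Result as written |
|---|---|
| Late parasitological failure | Met (parasitaemia after Day 7, no fever) |
| PCR-crude ACPR, Days 28/42/63 | Not achieved; crude ACPR does not separate new infection from recrudescence |
| Time to re-emergence | Event |
| Recrudescence | No; a different species is not the baseline clone |
| Re-infection exemption | Fits in substance, but needs PCR confirmation, and the baseline genotypes are falciparum by eligibility |
| Rescue criterion, Section 8.9 | Met, through the same classification |
| PCR-adjusted ACPR, Day 28 | Probably not a failure, but not stated; the rescue term could still remove ACPR |

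The falciparum-specific qPCR is taken only in patients over 5 years (Section 9.3.2), so it cannot settle the matter in the primary population.

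**2. Secondary endpoints.** Let c be crude ACPR without such infections and q the proportion of children acquiring one by the assessment day. If the two are independent, recorded crude ACPR is c(1 − q). The loss is c × q, which is at most q and close to q when c is high. The protocol gives no q. As illustration with an assumed q = 1% and the uncorrected Day 28 cure rates quoted in Section 4.2.2:
- c = 50.0%: 0.500 × 1% = 0.50 percentage points;
- c = 74.2%: 0.742 × 1% = 0.74 percentage points.

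q can only grow from Day 28 to Days 42 and 63.

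**3. The plan's own power figure.** Inputs (Sections 11.1 and 11.4.3.1): 150 evaluable patients per arm; true rate 96.4%; success if the two-sided 95% Clopper-Pearson lower limit exceeds 90%; futility looks at 50, 75, 100 and 125; Beta(9.5, 0.5) prior; stop if Pr(H0 | data) ≥ 0.30.
- The lower limit is 0.9062 at 143/150 and 0.8976 at 142/150. Success therefore needs at least 143 responders, or at most 7 failures.
- Without looks, P(X ≥ 143 | n = 150, p = 0.964) = 82.5%. The one-sided type I error at p = 0.90 is 1.40%.
- An arm continues with at least 46/50, 69/75, 91/100 and 114/125 responders.
- Exact convolution over all four looks gives power 81.7%, probability of a futility stop 4.1%, and type I error 1.36%.

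The stated figure of at least 80% reproduces.

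**4. Conditional sensitivity for the primary endpoint.** Suppose, contrary to the likelier reading, that these infections were scored as primary failures. The apparent response rate is then 0.964 × (1 − q), with q assumed:

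| Assumed q by Day 28 | Apparent rate | Power, four looks | Futility stop |
|---|---|---|---|
| 0 | 0.9640 | 81.7% | 4.1% |
| 0.5% | 0.9592 | 72.0% | 6.6% |
| 1% | 0.9544 | 61.3% | 10.0% |
| 2% | 0.9447 | 40.0% | 19.1% |
| 3% | 0.9351 | 23.0% | 31.1% |

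In 150 children, q = 1% is an expected 1.5 cases. The last two rows only extend the range; nothing in the protocol supports an incidence that high.

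**The case against.** **The primary endpoint is protected.** A reader might infer that the protocol scores every non-falciparum infection as a treatment failure, including in the primary analysis. It does not say so. The glossary removes confirmed new infections from failure, and Section 9.1.1 limits PCR-adjusted ACPR to the baseline clone, which another species cannot be. Meeting the late-failure wording proves nothing by itself, since every falciparum re-infection meets it too and PCR adjustment exists to override it. This stands. What remains is an unclassified case, not a stated failure.

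**PCR confirmation cuts both ways.** If falciparum genotyping yields nothing from such a sample, recrudescence is unconfirmed as well, and rules for indeterminate PCR often sit in the SAP. This is fair, and it supports calling the primary classification open. It does not help the crude and re-emergence definitions, which the protocol itself fixes.

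**The rescue route is not specific to species.** A child rescued for a falciparum re-infection meets the same clause. This is true, and a species qualifier alone would not close that route. The fix must therefore also address treatment given for the recurrence.

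**Crude ACPR and re-emergence count new infections by design, and are descriptive.** Correct, and no success threshold depends on them. But nothing suggests that they were meant to count infections with a parasite outside the objective.

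**The Asian patients.** A reader might extend the point to them. There are 21, and Section 11.3.2.1 keeps them out of the mITT population and hence the per-protocol population. They add no weight here.

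**Conclusion.** The point holds as a defect in the stated definitions. They restrict parasitaemia by stage but not by species, and they leave unused a species result that is recorded on every post-dose film. For PCR-crude ACPR at Days 28, 42 and 63 and for time to re-emergence, the consequence follows from the wording, and its size is about the incidence of non-falciparum infection, which is unknown from the protocol.

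For the primary endpoint the conclusion is weaker: the child is probably not a failure, but no rule settles it. The falls in power from 81.7% to 72.0% or 61.3% rest on two assumptions together: an incidence of 0.5% or 1%, and the new-infection clause not being applied. They show why the ambiguity should be closed in a design that tolerates 7 failures. They are not an expected loss, and the protocol's power statement is not wrong.

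**What to change.** - In the outcome classification, the glossary, flow-chart footnote d and Section 9.3.1.3, define parasitaemia, negative film, recurrence and failure **for efficacy** as asexual P. falciparum, using the thin-film species already recorded.
- State that a non-falciparum recurrence, and antimalarial treatment given for it, is not a treatment failure. Give one pre-stated rule for classifying such a child in the crude, adjusted and time-to-event analyses, for example censoring at that date in the time-to-event analyses.
- List these cases by arm, with species, day and any treatment given.
- Section 8.9 takes its rescue trigger from the same classification, so the two sections must be reconciled when the efficacy definitions change. This point concerns scoring only and takes no position on who should be treated.

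**Cost.** Wording in the protocol and SAP, with no new data collection. A few children may become non-evaluable or censored. The sample-size calculation is unchanged (82.5% power without looks, 81.7% with all four).
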